### 9.3.3 Removal of Subjects From Therapy or Assessment

The investigator may discontinue treating a subject with study treatment or withdraw the subject from the study at any time for safety or administrative reasons. The subject may decide to discontinue study treatment or withdraw from the study at any time for any reason.

The reason for discontinuation will be documented. If a subject discontinues study treatment, the subject will enter the Follow-Up Period and complete protocol-specified off-treatment visits, procedures, and survival follow-up unless the subject withdraws consent. The investigator should confirm whether a subject will withdraw from study treatment but agree to continue protocol-specified, off-treatment study visits, procedures, and survival follow-up, or whether the subject will withdraw consent. If a subject withdraws consent, the date will be documented in the source documents. The Subject Discontinuation From Treatment Phase CRF page will be completed indicating the reason for discontinuation. In addition, the date of last dose of study drug(s) will be recorded on the Study Drug Dosing CRF page.

During the Follow-Up Period, subjects who have discontinued study treatment before disease progression will continue to undergo tumor assessment every 8 weeks  $\pm$ 1 week until disease progression is documented or another anticancer therapy is initiated.

All subjects will be followed for survival until death, except where a subject withdraws consent or the sponsor chooses to halt survival follow-up after completion of the primary study analysis. Subjects will be followed for survival every 12 weeks  $\pm$ 1 week after the End of Treatment Visit. If a clinic visit is not feasible, follow-up information may be obtained via telephone or email.

A subject who discontinues study treatment should be followed for subsequent protocol-specified visits and procedures. If a subject discontinues study drug(s) but remains in the study, the set of End of Treatment procedures will be administered, and protocol-specified information will be collected. The reason for discontinuation from study drug(s) should be collected on the Subject Disposition From Treatment Phase CRF page. In addition, the date of last dose of study drug(s) will be recorded on the Study Drug Dosing CRF page. If a subject discontinues study treatment and the study at the same time, the end-of-study procedures (Final Visit) will be followed (see [Section 9.5.5](#)).

## **9.4 Treatments**

The study drugs under evaluation are lenvatinib in combination with everolimus.

### **9.4.1 Treatments Administered**

Lenvatinib will be provided as 4-mg and 10-mg capsules and everolimus will be provided as 5 mg tablets.

Initial doses of lenvatinib 18 mg/day (one 10-mg capsule and two 4-mg capsules) and everolimus 5 mg/day are to be taken orally in immediate succession once a day (QD), recommended approximately at the same time each morning (consistently either with or without food).

The following treatments will be administered to subjects in this study ([Table 1](#)).

**Table 1 Treatment Administered**

Drug Name	Strength	Oral Dose Form	Number Dispensed and Frequency	Duration a
Lenvatinib	10 mg	Capsule	1 × 10 mg capsule, once a day, recommended at approximately same time each morning	Daily
Lenvatinib	4 mg	Capsule	2 × 4 mg capsule, once a day, recommended at approximately same time each morning	Daily
Everolimus	5 mg	Tablet	1 × 5 mg tablet, once a day, recommended at approximately same time each morning	Daily

a. Subjects will continue to receive study treatment until disease progression, development of unacceptable toxicity, withdrawal of consent, or sponsor discontinuation.

#### 9.4.1.1 Criteria for Interruption of Treatment, Dose Reduction, and Resumption of Treatment

If a subject cannot tolerate lenvatinib due to its toxicities, the lenvatinib dose may be reduced, interrupted or discontinued according to the guidelines provided in Table 2 and Table 3. Lenvatinib dose reductions occur in succession based on the previous dose level, ie, one level at a time from 18 mg/day to 14, 10, and 8 mg/day. Any dose reduction below 8 mg/day must be discussed with the sponsor.

If a subject cannot tolerate everolimus due to its toxicities, the everolimus dose may be reduced, interrupted or discontinued. Everolimus dose may be reduced from 5 mg/day to 5 mg every other day.

Dose adjustments for both study drugs will be made according to the guidelines provided in Table 3 for management of intolerable toxicities. Investigators will decide the probability of the event being related to one or both drugs as to whether dose modification of one or both drugs is required. Once the dose has been reduced, it cannot be increased at a later date.

**Table 2 Dose Reduction Recommendations for Lenvatinib in Combination With Everolimus**

Initial Lenvatinib Dose (mg, QD)	Adjusted Dose To Be Administered (mg, QD)			
	Reduction 1	Reduction 2	Reduction 3	Reduction 4
18	14	10	8	a

QD = once daily.

a: Consult Sponsor for further dose reduction recommendations.

Refer to appropriate section for management of hypertension (Section 9.4.1.1.1), proteinuria (Section 9.4.1.1.2), hepatic injury (Section 9.4.1.1.3), thromboembolic events (Section 9.4.1.1.4), posterior reversible encephalopathy syndrome (PRES) (Section 9.4.1.1.5), hypocalcemia (Section 9.4.1.1.6), noninfectious pneumonitis (Section 9.4.1.1.7), infections (Section 9.4.1.1.8), and blood glucose / lipids (Section 9.4.1.1.9) before consulting the table below, as appropriate.

**Table 3 Lenvatinib-Everolimus Combination Therapy Dose Reduction and Interruption Instructionsa**

Lenvatinib/Everolimus Treatment-Related Toxicity b,c Including Hepatic Injury and Thromboembolic Events	During Therapy	Adjusted Dose
Grade 1 Tolerable Grade 2		
	Continue treatment	No change
Intolerable Grade 2c		
First occurrence	Interrupt lenvatinib and, if combination dosing, interrupt everolimus until resolved to tolerable Grade 2 or Grade 0-1	Dose reduction of lenvatinib (one dose reduction level, see Table 2 above) and, if combination dosing, resume everolimus at the same dose as prior to dose interruption.
Second occurrence (same toxicity or new toxicity)	Interrupt lenvatinib and, if combination dosing, interrupt everolimus until resolved to tolerable Grade 2 or Grade 0-1	Dose reduction of lenvatinib (one dose reduction level, see Table 2 above) and, if combination dosing, resume everolimus at the same dose as prior to dose interruption.
Third occurrence (same toxicity or new toxicity)	Interrupt lenvatinib and, if combination dosing, interrupt everolimus until resolved to tolerable Grade 2 or Grade 0-1	Dose reduction of lenvatinib (one dose reduction level, see Table 2 above) and, if combination dosing, resume everolimus at the same dose as prior to dose interruption.
Fourth occurrence (same toxicity or new toxicity)	Interrupt lenvatinib and, if combination dosing, interrupt everolimus until resolved to tolerable Grade 2 or Grade 0-1	Discuss with sponsor
Grade 3d,e		
First occurrence	Interrupt lenvatinib and, if combination dosing, interrupt everolimus until resolved to tolerable Grade 2 or Grade 0-1 f	Dose reduction of lenvatinib (one dose reduction level, see Table 2 above) and, if combination dosing, resume everolimus at the same dose as prior to dose interruption.
Second occurrence (same toxicity or new toxicity)	Interrupt lenvatinib and, if combination dosing, interrupt everolimus until resolved to tolerable Grade 2 or Grade 0-1 f	Investigator to decide the probability of the event being related to 1 or both drugs as to whether dose modification of 1 or both drugs was required. Dose reduction of lenvatinib (one dose reduction level, see Table 2 above) and/or reduce everolimus to 5 mg every other day.
Third occurrence (same toxicity or new toxicity)	Interrupt lenvatinib and, if combination dosing, interrupt everolimus until resolved to tolerable Grade 2 or Grade 0-1 f	Investigator to decide the probability of the event being related to 1 or both drugs as to whether dose modification of 1 or both drugs was required. Dose reduction of lenvatinib (one dose reduction level, see Table 2 above) and/or adjust everolimus as follows: i) if 5 mg daily everolimus at event onset, reduce to 5 mg every other day, or ii) if 5 mg every other day everolimus at

**Table 3 Lenvatinib-Everolimus Combination Therapy Dose Reduction and Interruption Instructionsa**

Lenvatinib/Everolimus Treatment-Related Toxicity b,c Including Hepatic Injury and Thromboembolic Events	During Therapy	Adjusted Dose
		event onset, discontinue.
Fourth occurrence	Interrupt lenvatinib and everolimus	Discuss with sponsor
Grade 4g: Discontinue lenvatinib and everolimus		

Note: For grading see Common Terminology Criteria (CTC) for Adverse Events (AE) version 4.03. Collect all CTC grades of AEs, decreasing and increasing grade.

a: A delay of lenvatinib/ everolimus treatment for more than 28 days (due to lenvatinib/ everolimus-related toxicities) requires a discussion with the sponsor before treatment may be resumed.

b: Excluding alopecia. Drug interruption and dose reduction may be initiated for intolerable Grade 2 and Grade 3 related symptoms such as anemia, lymphocytopenia, asymptomatic neutropenia if there are no other treatment options available and the investigator considers that dose interruption or reduction of study medication is the only remaining alternative. Optimal medical management for nausea, vomiting, and/or diarrhea have to be initiated prior to any lenvatinib/ everolimus interruption or dose reduction.

c: Applicable only to Grade 2 toxicities judged by the subject and physician to be intolerable. If Grade 2 toxicity is determined to be intolerable, the dose of study drug will be reduced with or without dose interruption. Interruption for Grade 3 toxicities is mandatory.

d: Obese subjects with weight loss requiring dose interruption and reduction do not need to return to baseline or Grade 1 weight loss to restart lenvatinib. Based on the judgment of the investigator, subjects may be restarted at the lower dose of lenvatinib once the weight has been stable for at least 1 week. Normal body mass index (BMI) should be used as the new baseline for future dose reductions.

e: Not applicable to abnormal clinical laboratory values that are not clinically relevant based on the judgment of the investigator (eg, alanine aminotransferase (ALT), aspartate aminotransferase (AST), gamma glutamyl transpeptidase ( $\gamma$ -GTP) values  $< 10 \times$  upper limit of normal (ULN), and Na).

f: For hematologic toxicities, restart treatment after toxicity resolves to Grade 2.

g: Excluding laboratory abnormalities judged to be nonlife-threatening, in which case have to be managed as Grade 3.

#### 9.4.1.1.1 MANAGEMENT OF HYPERTENSION

Lenvatinib-everolimus combination therapy should be withheld in any instances where a subject is at imminent risk to develop a hypertensive crisis or has significant risk factors for severe complications of uncontrolled hypertension (eg, BP significantly  $\geq 160/100$  mmHg, significant risk factors for cardiac disease, intracerebral hemorrhage, or other significant comorbidities). Once the BP is controlled, lenvatinib-everolimus combination therapy should be resumed as described below.

The following guidelines should be followed for the management of systolic BP  $\geq 140$  mmHg up to  $< 160$  mmHg or diastolic BP  $\geq 90$  mmHg up to  $< 100$  mmHg confirmed on repeat measurements after an hour, for subjects receiving lenvatinib-everolimus combination therapy:

- Continue lenvatinib-everolimus combination therapy and institute antihypertensive therapy for subjects not already receiving this.

- For subjects already on antihypertensive medication, the dose of the current agent may be increased, if appropriate, or one or more agents of a different class of antihypertensive should be added.

The following guidelines should be followed for the management of systolic BP  $\geq$  160 mmHg or diastolic BP  $\geq$  100 mmHg confirmed on repeat measurements after an hour, for subjects receiving lenvatinib-everolimus combination therapy:

- If systolic BP  $\geq$  160 mmHg or diastolic BP  $\geq$  100 mmHg persists despite maximal antihypertensive therapy, then lenvatinib-everolimus combination therapy administration should be interrupted and restarted when BP  $\leq$  150/95 mmHg at a dose of: one level of dose reduction (ie, 14-mg once daily) per Table 3 of lenvatinib. Resume everolimus at the same dose as prior to dose interruption.
  - If systolic BP  $\geq$  160 mmHg or diastolic BP  $\geq$  100 mmHg recurs on the first reduced dose (ie, 14-mg once daily) despite optimal management of hypertension with antihypertensive medications (either by dose increase or the addition of a different class of antihypertensive), then lenvatinib-everolimus combination therapy administration should be interrupted and restarted when BP  $\leq$  150/95 mmHg at a dose of: one level of dose reduction (ie, 10 mg once daily) per Table 2 and Table 3 of lenvatinib. Resume everolimus at the same dose as prior to dose interruption.
  - If systolic BP  $\geq$  160 mmHg or diastolic BP  $\geq$  100 mmHg recurs on the next reduced dose (ie, 10 mg once daily) despite optimal management of hypertension with antihypertensive medications (either by dose increase or the addition of a different class of antihypertensive), then lenvatinib-everolimus combination therapy administration should be interrupted and restarted when BP  $\leq$  150/95 mmHg at a dose of: one level of dose reduction (ie, 8 mg once daily) per Table 2 and Table 3 of lenvatinib. Resume everolimus at the same dose as prior to dose interruption.
  - Additional dose reduction should be discussed with the sponsor.

The following guidelines should be followed for the management of Grade 4 hypertension (life-threatening consequences):

- Institute appropriate medical management.
- Discontinue lenvatinib-everolimus combination therapy.

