### Management of Hypertension

Lenvatinib-everolimus combination therapy should be withheld in any instance where a subject is at imminent risk to develop a hypertensive crisis or has significant risk factors for severe complications of uncontrolled hypertension (eg, BP significantly  $\geq 160/100$  mmHg, significant risk factors for cardiac disease, intracerebral hemorrhage, or other significant comorbidities). Once the BP is controlled, lenvatinib-everolimus combination therapy should be resumed as described below.

The following guidelines should be followed for the management of systolic BP  $\geq 140$  mmHg up to  $< 160$  mmHg or diastolic BP  $\geq 90$  mmHg up to  $< 100$  mmHg confirmed on repeat measurements after an hour, for subjects receiving lenvatinib-everolimus combination therapy:

- Continue lenvatinib-everolimus combination therapy and institute antihypertensive therapy for subjects not already receiving this.
- For subjects already on antihypertensive medication, the dose of the current agent may be increased, if appropriate, or one or more agents of a different class of antihypertensive should be added.

The following guidelines should be followed for the management of systolic BP  $\geq 160$  mmHg or diastolic BP  $\geq 100$  mmHg confirmed on repeat measurements after an hour, for subjects receiving lenvatinib-everolimus combination therapy:

- If systolic BP  $\geq 160$  mmHg or diastolic BP  $\geq 100$  mmHg persists despite maximal antihypertensive therapy, then lenvatinib-everolimus combination therapy administration should be interrupted and restarted when BP  $\leq 150/95$  mmHg at a dose of: one level of dose reduction (ie, 14-mg once daily) per Table 2 of lenvatinib. Resume everolimus at the same dose as prior to dose interruption.
  - If systolic BP  $\geq 160$  mmHg or diastolic BP  $\geq 100$  mmHg recurs on the first reduced dose (ie, 14-mg once daily) despite optimal management of hypertension with antihypertensive medications (either by dose increase or the addition of a different class of antihypertensive), then lenvatinib-everolimus combination therapy administration should be interrupted and restarted when BP  $\leq 150/95$  mmHg at a dose of: one level of dose reduction (ie, 10-mg once daily) per Table 1 and Table 2 of lenvatinib. Resume everolimus at the same dose as prior to dose interruption.

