#### 9.4.1.1.7 MANAGEMENT OF NONINFECTIOUS PNEUMONITIS

Noninfectious pneumonitis is a recognized class effect of rapamycin derivatives, including everolimus. Noninfectious pneumonitis (including interstitial lung disease) was described in 12% of subjects taking everolimus. Some cases were severe and on rare occasions, a fatal outcome was observed. Investigators should therefore consider a diagnosis of noninfectious pneumonitis in subjects presenting with nonspecific respiratory signs and symptoms and in whom infectious, neoplastic and other nonmedicinal causes have been excluded by means of appropriate investigations.

Guidelines for assessment and management of noninfectious pneumonitis are summarized as follows for subjects receiving lenvatinib-everolimus combination therapy:

- Subjects who develop radiological changes suggestive of noninfectious pneumonitis and have few or no symptoms (CTCAE Grade 1) may continue lenvatinib-everolimus combination therapy without dose adjustments.
- If symptoms are CTCAE Grade 2:
  - Starting dose of lenvatinib combination therapy with 5 mg daily everolimus: combination therapy should be interrupted and the use of corticosteroids may be indicated until symptoms abate (resolved to CTCAE Grade 0-1 or baseline) and may be restarted with 5 mg everolimus daily in combination with lenvatinib (ie, lenvatinib reinitiated at the same dose as prior to dose interruption) administered daily. Discontinue everolimus if failure to recover within 4 weeks of reinitiating treatment, and continue lenvatinib as a single agent therapy depending on individual clinical circumstance.
  - If Grade 2 noninfectious pneumonitis recurs despite optimal management, then lenvatinib-everolimus combination therapy administration should be interrupted and the use of corticosteroids may be indicated until symptoms abate (resolved to CTCAE Grade 0-1 or baseline). Lenvatinib may be reinitiated as a single agent therapy depending on individual clinical circumstances.
- If symptoms are CTCAE Grade 3:
  - Starting dose of lenvatinib combination therapy with 5 mg daily everolimus: combination therapy should be interrupted and the use of corticosteroids may be indicated until clinical symptoms resolve. Lenvatinib may be reinitiated as single agent therapy depending on the individual clinical circumstances.
- If symptoms are CTCAE Grade 4:
  - Study medications should be discontinued.

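### The hypertension and Grade 2 pneumonitis restart doses fit only subjects with no earlier reduction; for the others they conflict with the no-increase rule or leave a gap

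*Protocol*

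**What the plan says.** Section 9.4.1.1 sets two general rules. Lenvatinib reductions are relative: "Lenvatinib dose reductions occur in succession based on the previous dose level", that is, "one level at a time from 18 mg/day to 14, 10, and 8 mg/day". In the paragraph covering both drugs it adds: "Once the dose has been reduced, it cannot be increased at a later date". The same section gives everolimus one reduced level, 5 mg every other day.

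Section 9.4.1.1.1 handles persistent hypertension in three steps. The first restart is "at a dose of: one level of dose reduction (ie, 14-mg once daily) per Table 3 of lenvatinib". The second applies if hypertension "recurs on the first reduced dose (ie, 14-mg once daily") and leads to 10 mg. The third starts from 10 mg and leads to "one level of dose reduction (ie, 8 mg once daily) per Table 2 and Table 3 of lenvatinib". Further reduction is to be discussed with the sponsor. Everolimus resumes at its pre-interruption dose. The Synopsis has the same steps, with the first as "one level of dose reduction (ie, 14-mg once daily) per Table 2 of lenvatinib", where the tables are numbered one lower.

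Section 9.4.1.1.7 says that after Grade 2 noninfectious pneumonitis treatment "may be restarted with 5 mg everolimus daily in combination with lenvatinib", with lenvatinib at its pre-interruption dose. The branch is introduced by reference to a starting dose that includes everolimus 5 mg daily. The Synopsis repeats this.

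The text under Table 2 of the main protocol sends sites to these event-specific sections before they use the general instructions in Table 3.

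**The concern.** The event-specific sections appear to be written for a subject who reaches the event with no earlier dose reduction. Table 3 reduces lenvatinib at the first intolerable Grade 2 or first Grade 3 treatment-related toxicity, and allows everolimus to be reduced from the second Grade 3 occurrence. Subjects can therefore reach a first hypertension or pneumonitis event below the starting dose.

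For them, a site that follows the milligram figure and a site that follows the relative wording would restart at different doses after a toxicity. One literal reading raises a dose that the general rule says may not be raised. What is at stake is subject safety and uniform conduct across about 8 sites.

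**Working it through.** **Inputs.** Lenvatinib ladder 18, 14, 10, 8 mg, then sponsor consultation (Section 9.4.1.1 and Table 2). First hypertension restart: one level down, glossed as 14 mg (Section 9.4.1.1.1). Everolimus levels: 5 mg daily and 5 mg every other day (Section 9.4.1.1). Grade 2 pneumonitis restart: everolimus 5 mg daily (Section 9.4.1.1.7).

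**Hypertension, first event.** The check compares one level down the ladder with the figure in parentheses. Change = 14 minus current dose; ratio = 14 / current dose.

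| Lenvatinib dose at onset | One level down | Figure in parentheses | Change under the figure |
|---|---|---|---|
| 18 mg | 14 mg | 14 mg | 14 − 18 = −4 mg; the two agree |
| 14 mg | 10 mg | 14 mg | 14 − 14 = 0; 14/14 = 1.00 |
| 10 mg | 8 mg | 14 mg | 14 − 10 = +4 mg; 14/10 = 1.40 |
| 8 mg | sponsor consultation | 14 mg | 14 − 8 = +6 mg; 14/8 = 1.75 |

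The protocol's figure is reproduced in the first row only. In the second row it contradicts the one-level wording but does not breach the no-increase rule. In the third and fourth rows it contradicts both.

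**Hypertension, later steps.** These name the dose at which hypertension recurs (14, then 10 mg) and the next dose (10, then 8 mg). Matched by milligrams, they agree with the ladder. They are worded for recurrence, however, so they do not clearly cover a first hypertension event in a subject brought to 14 or 10 mg by another toxicity. They also equate the first reduced dose with 14 mg.

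**Grade 2 pneumonitis.** Everolimus 5 mg every other day averages 5/2 = 2.5 mg per day. A restart at 5 mg daily gives 5/2.5 = 2.0 times that dose. The branch heading has two possible readings:

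- The dose at which the subject started the study. This is 5 mg daily for everyone, so the branch covers a subject since reduced to every other day, and the restart conflicts with the no-increase rule.
- The dose at event onset. The branch then covers only subjects on daily dosing, and no branch tells a site how to restart an every-other-day subject after a first Grade 2 event.

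Table 3 distinguishes the two everolimus levels explicitly by dose at event onset in its third Grade 3 row. The pneumonitis section does not use that wording.

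Lenvatinib raises no conflict in the pneumonitis rule, and everolimus raises none in the hypertension rule: each resumes at its pre-interruption dose.

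**The case against.** The strongest reply is that the hypertension rule is relative. Its operative words call for one level of reduction and refer to the dose tables; Section 9.4.1.1 makes reductions relative to the previous level and forbids increases. A careful site would treat 14 mg as an illustration for a subject on 18 mg. Nothing in either event section disclaims the no-increase rule. The proteinuria section, by contrast, says explicitly that its everolimus instruction replaces Table 3. The pneumonitis wording is also permissive.

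Much of this stands. A reader might infer that the protocol orders re-escalation after hypertension. It does not: it gives two instructions that diverge once a subject has been reduced, and the relative one agrees with the general rule. A reader might also count a 14 mg restart from 14 mg as a breach of the no-increase rule. It is not an increase, and conflicts only with the one-level wording. The pneumonitis rule may be a gap and not a contradiction.

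What does not stand is that the text is therefore clear. The figure is introduced as an equivalence, not as an example. Sites are sent to the event sections first, and the proteinuria section shows that such a section can override Table 3. No sentence says which prevails when a specific milligram figure meets the general rule.

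**Conclusion.** This is an internal contradiction in the hypertension rule and, depending on how its heading is read, a contradiction or an omission in the Grade 2 pneumonitis rule. It affects only subjects with an earlier reduction: of lenvatinib for hypertension, of everolimus for pneumonitis. Per subject, the literal figures mean no change from 14 mg, +40% from 10 mg, +75% from 8 mg, and a doubling of everolimus from every-other-day dosing. These sizes assume that the milligram figure is followed over the relative wording or, for pneumonitis, that the branch covers all subjects.

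The number of subjects affected cannot be derived. A reader might apply the 71% rate of Grade 3 and 4 events on the combination in Study 205 (Section 7.1.4.2) to the 31 planned subjects. That does not count the exposed group. It includes Grade 4 events, which generally lead to discontinuation; it is not limited to treatment-related toxicity, to which Table 3 applies; and it says nothing about who later has hypertension or pneumonitis. A lenvatinib reduction is also irrelevant to the everolimus conflict.

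A reader might further infer that the exposure-response analyses would become uninterpretable. The protocol does not support this: it summarises the quantity of each drug given and derives exposure from a population pharmacokinetic model. The Simon design, its sample size and its error rates are not affected.

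The correction should still be made, because the conflict concerns restart after toxicity and is easily removed.

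**What to change.** Reconcile Sections 9.4.1.1.1 and 9.4.1.1.7, and the matching Synopsis text on hypertension and noninfectious pneumonitis, with Section 9.4.1.1. For each event, state the restart instruction by dose at event onset (lenvatinib 18, 14, 10 or 8 mg; everolimus 5 mg daily or 5 mg every other day), so that every combination leads to one instruction. State whether the pneumonitis heading refers to the study starting dose or to the dose at onset. Either uphold the no-increase rule throughout or name the exceptions to it. The clinical team decides the content; this review takes no position on which dose or rule is right.

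The cost is a wording amendment in two subsections and their Synopsis copies. It needs no added subjects or data collection and no change to the statistical design.
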